**Withdraw criteria:**

- 1- Participant decides to withdraw
- 2- Participant experiencing adverse events such as pain, coughing, or discomfort.

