## Abstract

**Background:** High-flow nasal cannula (HFNC) is a device that can reduce the work of breathing (WOB) and improve oxygenation by providing a flow that matches or exceeds patient's peak inspiratory flow during tidal breathing. Despite its widespread use, there remains a lack of consensus regarding the optimal flow settings. Two new HFNC devices that can provide information regarding patient's peak tidal inspiratory flow breath by breath are recently available, which might help guide set and titrate the flow settings. This study aims to investigate the effects of different flow settings on lung impedance in a cohort of healthy volunteers by using the two new HFNC devices.

**Methods:** This prospective, randomized crossover trial will enroll adult healthy volunteers. Initially, the subject's peak inspiratory flow will be measured using a mask connected with a respiratory monitor. Subsequently, the volunteers will undergo HFNC treatment at different flow settings while their peak inspiratory flow will be continuously monitored. The primary outcome of this study is the lung aeration with different flow settings. Secondary outcomes include the lung aeration with different devices, subject's comfort at different flow settings, and the correlation between the subject's peak inspiratory flow measured by HFNC and by a mask connected with a respiratory monitor.

**Results:** N/A

**Conclusion:** N/A

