## Introduction

High-flow nasal cannula (HFNC) is a widely used medical device. It can deliver flows up to 60-100 liter per minute (LPM) and maintain a consistent fraction of inspired oxygen once the set flow exceeds the patient's tidal inspiratory flow (PTIF). HFNC has demonstrated effectiveness in reducing the risk of intubation in patients with hypoxic respiratory failure, and can improve ventilation in patients with chronic obstructive pulmonary disease. These effects can be attributed to the many benefits offered by the device, including improving ventilation/prefusion matching, reducing the work of breathing, and washing out the dead space of the upper airway. Furthermore, when the flow exceeds the PTIF, a positive end-expiratory pressure (PEEP) effect is observed. This PEEP effect can be estimated by measuring the end-expiratory lung impedance (EELI), which is reported to be correlated with HFNC flows. Despite recommendations that the set flow should match or exceed the PTIF, continuous measurement of PTIF, especially during HFNC treatment, remains challenging, and there is no consensus on optimal flow settings. Therefore, a continuous PTIF monitoring could serve as an objective reference for practitioners when determining the initial flow and flow titration for different patients and under different conditions.

Two new HFNC devices, the *OmniOx HFT7500* (MEK, Paju-si, South Korea) and the *Airvo3* (Fisher & Paykel Healthcare Ltd, Auckland, New Zealand), could potentially provide the solution. The *HFT7500* can continuously measure PTIF during therapy, while *Airvo 3* provides a continuous waveform reading of the targeted flow to assess if it meets patient's demand. However, the accuracy and effectiveness of these devices remain unknown. Thus, in our study, we will measure the participants' PTIF via a mask prior to applying the HFNC and compare the flows with those displayed by the HFNC devices during treatment, particularly at different flow settings. We will also measure the lung aeration of different flows using the two devices. Our aim is to investigate the effects of different flows on the homogeneity of lung aeration. Our hypothesis is that as flow setting increases, lung aeration (EELI) will also increase.

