**Study Procedure:**

- 1- Study will be advertised at Rush University through a poster in a public place
- 2- Interested participants can contact the study investigator ([name]) through email or phone call which will be provided in the advertisement

- 3- Interested participants will be assessed for eligibility. If eligible, the study investigator will explain the whole study procedure and the benefits/harms to them in a private room, questions will be answered. Next, participants will be given a minimum of 30 mins to consider participating in the study. Consent will be obtained.
- 4- At the beginning, an electronic impedance tomography belt will be placed around the torso of the subjects according to their chest size. The participants will rest in a bed with head elevated at 30 degree.
- 5- Baseline measurement over 5 minutes of respiratory rate, tidal volume and PTIF will be obtained using a respiratory monitor (NICO2, Respiration, Murrysville, PA, USA) through a mask. Then the subject will be coached to breathe normally with room air for 20 mins, at the end, they will be questioned about their comfort level using a visual numerical scale ranging between 0 (extreme discomfort) and 10 (very comfortable).
- 6- HFNC devices ([HFT700](#)[HFT750](#) and Airvo 3) will be applied, three different flows will be utilized at a random sequence: 20, 40, and 60 L/min. Each flow will be utilized for 20 mins. There is a 5 min break between flows. HFNC will be removed during the break.
- 7- Between flow settings, PTIF will be measured via the mask and respiratory monitor
- 8- PTIF (measured by the [HFT700](#)[HFT750](#)) or targeted flow waveform (using Airvo 3), EELI, and respiratory rate will be monitored continuously through the procedure, and comfort level will be assessed at the end of each flow setting
- 9- The whole procedure is expected to last 3-4 hours

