## **Data Collection:**

All the following data will be collected from the participant and/or during the study.

**Demographic variables:** Age, sex, and ethnicity

**Anthropometric variables:** Height, weight

**Study variables:** Baseline PTIF, respiratory rate and tidal volume via NICO2 (Respironics, Murrysville, PA, USA). Continuous monitoring of PTIF, and respiratory rate during 3 different flow settings via two HFNC devices. Comfort level reported by participants using a visual numerical scale ranging between 0 (extreme discomfort) and 10 (very comfortable) at the end of each flow setting. Quantifying aeration homogeneity using electronic impedance tomography device by assessing EELI, regions of interest (ROI1, ROI2, ROI3, ROI4), and center of ventilation (CoV) during the 3 different flow settings.

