## **Data Analysis**

Kolmogorov-Smirnov will be used to test the normality of distribution for continuous variables. Based on the distribution of the variables, continuous variables (respiratory rate, PTIF and comfort level) will be reported as mean and standard deviation (SD) or median and Inter-Quartile Range (IQR). Friedman or Repeated Measures ANOVA analysis will be used to compare the differences of continuous variables between baseline and 3 flow settings with each HFNC device. Mann-Whitney or independent t test will be used to compare the differences of continuous variables between two devices. Spearman's Rho or Pearson Correlation statistical test will be used to assess the correlation between PTIF measured via mask (NICO2) with PTIF measured by the HFT7~~500~~ device. A *p*-value of < 0.05 will be considered statistically significant. Data analysis will be conducted with SPSS software (SPSS 26.0; Chicago, IL).

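### A participant withdrawn part-way through a device drops out of that device's whole flow comparison, because the planned Friedman or repeated measures ANOVA needs complete rows and the plan has no rule for recorded EELI

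*Combined protocol and SAP*

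**What the plan says.** - **Primary outcome.** The Abstract states: "The primary outcome of this study is the lung aeration with different flow settings". The Introduction ties this to EELI, with the hypothesis that "as flow setting increases, lung aeration (EELI) will also increase".
- **Recording.** Study Procedure gives 20, 40 and 60 L/min in random order, 20 minutes each, after a baseline that always comes first. Step 8 adds that "EELI, and respiratory rate will be monitored continuously through the procedure". When a person stops, EELI from baseline and from every finished setting already exists.
- **Withdrawal.** The second criterion is "Participant experiencing adverse events such as pain, coughing, or discomfort". It acts on the participant. The section does not provide for ending one setting and continuing with the next, and does not say what happens to data already recorded.
- **Test.** Data Analysis says that "Friedman or Repeated Measures ANOVA analysis will be used" for differences "between baseline and 3 flow settings with each HFNC device". Its bracketed list of continuous variables names respiratory rate, PTIF and comfort level, but not EELI.
- **Silence.** No section covers missing settings, retention of data recorded before withdrawal, replacement of participants or an expected loss rate. The sample size of 26 states no allowance for losses. The Data Collection list has no item for the reason for a stop.

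**The concern.** Friedman's test and classical repeated measures ANOVA work on complete blocks. Here a block is one person's baseline, 20, 40 and 60 L/min values on one device. If one value is missing, the other three leave that test as well. The withdrawal rule produces exactly this pattern, because a stop at one setting also removes all later settings.

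The first cost is precision: good EELI data from completed 20-minute settings go unused. The second is possible selection: each device's flow comparison describes only people who completed every flow on that device. If the tendency to stop depends on flow and is related to how much EELI rises, the estimated flow effect is biased. Without a prespecified rule, the handling of these people would be settled after it is known who stopped, and on the primary outcome.

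**Working it through.** **1. What a stop removes from one device's test.** A row holds four values: baseline and three flows.

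| Stop occurs during | Completed values in the row | Used by the planned test |
|---|---|---|
| first setting | 1 (baseline) | 0 |
| second setting | 2 (baseline + 1 flow) | 0 |
| third setting | 3 (baseline + 2 flows) | 0 |

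The test is run separately for each device, so a person who finished one device and stopped on the other keeps the first row intact.

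**2. Does each person use both devices?** This is not stated outright. Baseline takes 5 + 20 = 25 minutes. Two devices need 25 + 6×20 + 5×5 = 170 minutes; one device needs 25 + 3×20 + 2×5 = 95 minutes. The stated 3-4 hours fits two devices better. The complete-row problem exists either way.

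**3. The plan's figure of 26.** The Sample size section gives changes from baseline of 1.12 (0.8, 2.01) and 1.44 (1.05, 2.16), a difference of 0.32, with 95% confidence and 80% power. The brackets are not labelled, and no within-person correlation or sidedness is given. I use n = [(1.96 + 0.84) × SD of difference / 0.32]², with correlation 0.5 as an assumption.

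- Brackets read as mean ± SD: SDs are 1.21/2 = 0.605 and 1.11/2 = 0.555, the SD of the difference is 0.582, and n = 26 (28 with the t distribution).
- Brackets read as an interquartile range: SDs are 1.21/1.35 = 0.896 and 1.11/1.35 = 0.822, the SD of the difference is 0.862, and n = 57 (59 with t).

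So 26 can be reached under particular assumptions, but the documents do not fix it. The next steps take it at face value.

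**4. Precision.** The standardised paired difference that gives exactly 80% power at n = 26 (two-sided 0.05, noncentral t) is 0.572, which implies an SD of the difference of 0.32/0.572 = 0.56. Loss rates are assumptions.

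| Assumed loss | Complete rows | Power |
|---|---|---|
| none | 26 | 80.0% |
| 5% | 25 | 78.3% |
| 10% | 23 | 74.6% |
| 20% | 21 | 70.3% |
| 30% | 18 | 62.8% |

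These figures apply to the 0.32 contrast between two flows.

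**5. Selection, as a sensitivity range only.** Suppose a fraction p stops, and that the tendency to stop has correlation r with the EELI change. Under a normal model the mean among completers shifts by −r × φ(z) / (1 − p) standard deviations, with z the (1 − p) normal quantile.

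| p | r | Shift (SD) | Shift × 0.56 | Share of 0.32 |
|---|---|---|---|---|
| 10% | 0.3 | −0.3×0.1755/0.9 = −0.0585 | −0.033 | 10% |
| 10% | 0.5 | −0.0975 | −0.055 | 17% |
| 20% | 0.3 | −0.3×0.2800/0.8 = −0.105 | −0.059 | 18% |
| 20% | 0.5 | −0.175 | −0.098 | 31% |

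The planned test also includes baseline. Holding the SD at 0.56, the same shifts are 0.033/1.44 = 2% to 0.098/1.12 = 9% of the changes from baseline. With r = 0 the shift is zero; with r negative its sign reverses. The documents supply neither p nor r.

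**The case against.** Several objections have force.

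- **EELI is not named in Data Analysis, and no section says that recorded data are discarded.** Both are true. The loss follows from the complete-row requirement of the test. That test is the only planned one that can serve the flow comparison, and the Outcomes section lists EELI for that comparison. If it was not meant for EELI, the primary outcome has no planned flow test, and the same edit settles that.
- **The withdrawal criterion may be read too strictly.** It has no severity threshold, and comfort is scored at the end of each setting on a scale that runs down to extreme discomfort. The protocol therefore seems to expect some discomfort to be carried through a setting. How these two sections fit together is for the sponsor to reconcile. It affects how often stops occur, not what the test does with them.
- **A reader might infer that all EELI recorded on a withdrawn person is lost.** It is not. A finished device keeps its complete row, and the between-device Mann-Whitney or independent t tests need no complete rows.
- **A reader might infer that the result rests on volunteers who tolerate 60 L/min in particular.** Completers have, of course, completed 60 L/min, but nothing in the documents ties stops to that flow or to EELI response.
- **A reader might infer that the second device loses more people, so that the two devices describe different populations.** The order of devices is not stated. If it varies between people, each device comes second for some of them.
- **A reader might infer that losses could not be traced to a flow afterwards.** Continuous recording shows where a stop occurred; only the reason lacks a listed field.

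What remains is the discarding of completed settings within an unfinished device. That comes from the choice of test, so it is more than a missing detail.

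**Conclusion.** The point holds in this form: taken together, the participant-level withdrawal rule and a complete-row test exclude completed EELI settings from the primary comparison for anyone who stops part-way through a device.

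The size is conditional. With no stops there is no effect. If stopping is unrelated to EELI response, the cost is precision only: about 75% power with 23 complete rows and 70% with 21, provided that 26 gives exactly 80%. If it is related, there is bias of unknown direction and size. The range of 10-31% of the 0.32 contrast, or about 2-9% of the changes from baseline, rests on an assumed stop rate, an assumed correlation and a back-solved SD. It should not be read as an estimate for this trial. The change is still worth making before data are seen, because it is cheap and concerns the primary outcome.

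**What to change.** Leave the clinical stopping rule unchanged and amend the data rules.

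1. **Data Analysis.** Name EELI as the primary variable. Replace the complete-row test with a linear mixed model on change from baseline: participant random; flow, order among the HFNC periods and, if each person uses both devices, device as fixed effects; transformed values if non-normal. State that every completed setting is used, including those of participants later withdrawn. Order must cover the HFNC periods only. Baseline always comes first, so a period term that included it could not be separated from the comparison with baseline.
2. **Interrupted settings.** Use EELI from a setting stopped early only in a sensitivity analysis, with a window fixed in advance, since the event that caused the stop may disturb the signal.
3. **Data Collection and reporting.** Record the reason for each stop, and report stops by flow and device beside the EELI result.

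The cost is protocol wording, one extra data item and slightly more analysis work; mixed models are available in the SPSS version named. No extra participants or procedures are needed. Two limits remain. The model assumes that settings are missing at random, so it does not remove bias if stopping depends on EELI that was never observed. A person who stops during the very first setting still contributes no completed change from baseline.

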## **Data Collection:**

All the following data will be collected from the participant and/or during the study.

**Demographic variables:** Age, sex, and ethnicity

**Anthropometric variables:** Height, weight

**Study variables:** Baseline PTIF, respiratory rate and tidal volume via NICO2 (Respironics, Murrysville, PA, USA). Continuous monitoring of PTIF, and respiratory rate during 3 different flow settings via two HFNC devices. Comfort level reported by participants using a visual numerical scale ranging between 0 (extreme discomfort) and 10 (very comfortable) at the end of each flow setting. Quantifying aeration homogeneity using electronic impedance tomography device by assessing EELI, regions of interest (ROI1, ROI2, ROI3, ROI4), and center of ventilation (CoV) during the 3 different flow settings.

## **Outcomes**

- Lung aeration, EELI, respiratory rate, and comfortable level compared at baseline (without HFNC device) with 3 different flow settings
- Lung aeration, EELI, respiratory rate, and comfortable level between two HFNC devices (Airvo 3 vs HFT7500)
- PTIFs measured by the mask with respiratory monitor and by the HFT7500 device during the HFNC treatment at three flow settings.
- PTIFs measured by the mask with respiratory monitor and PTIF waveform monitored by the Airvo 3 device during the HFNC treatment at three flow settings.

## **Data Analysis**

Kolmogorov-Smirnov will be used to test the normality of distribution for continuous variables. Based on the distribution of the variables, continuous variables (respiratory rate, PTIF and comfort level) will be reported as mean and standard deviation (SD) or median and Inter-Quartile Range (IQR). Friedman or Repeated Measures ANOVA analysis will be used to compare the differences of continuous variables between baseline and 3 flow settings with each HFNC device. Mann-Whitney or independent t test will be used to compare the differences of continuous variables between two devices. Spearman's Rho or Pearson Correlation statistical test will be used to assess the correlation between PTIF measured via mask (NICO2) with PTIF measured by the HFT7~~500~~ device. A *p*-value of < 0.05 will be considered statistically significant. Data analysis will be conducted with SPSS software (SPSS 26.0; Chicago, IL).

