**Exclusion criteria:**

- 1- Chronic pulmonary diseases, including COPD, interstitial lung disease, cystic fibrosis, etc.
- 2- Uncontrolled asthma;
- 3- Pregnancy
- 4- Subjects who have cold/flu symptoms (sore throat, runny nose, fever, chills, coughing)
- 5- Nose abnormalities that can affect the functionality of the nasal prongs

**Sample size:** 26 subjects

This study is a single group comparison study designed to compare the change of EELI with different flow settings during HFNC treatment. In the study by Plotnikow et al that compared HFNC flows of 30 vs 50 L/min, they reported that mean changes of EELI from baseline were 1.12 (0.8, 2.01) at 30 L/min and 1.44 (1.05, 2.16) at 50 L/min. We use this result to calculate the sample size, with confidence level (1 -  $\alpha$ ) of 95% and power (1 -  $\beta$ ) of 80%, the sample size is calculated to be 26.

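### The primary question is whether EELI rises with flow, but the only planned cross-flow test is unordered, can be read as including a non-randomised baseline, and has no flow contrast or follow-up rule

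*Combined protocol and SAP*

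**What the plan says.** The Abstract states: "The primary outcome of this study is the lung aeration with different flow settings". The Introduction gives the direction: "Our hypothesis is that as flow setting increases, lung aeration (EELI) will also increase". The Sample size paragraph describes a study "designed to compare the change of EELI with different flow settings during HFNC treatment" and takes its inputs from an earlier study in which "mean changes of EELI from baseline were 1.12 (0.8, 2.01) at 30 L/min and 1.44 (1.05, 2.16) at 50 L/min". All three concern one flow against another.

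Study Procedure step 5 puts the room-air period before any HFNC: "Then the subject will be coached to breathe normally with room air for 20 mins". In step 6 only the flows are put in random order: "three different flows will be utilized at a random sequence: 20, 40, and 60 L/min".

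The Outcomes section lists EELI, among other variables, "compared at baseline (without HFNC device) with 3 different flow settings".

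For comparisons across conditions, Data Analysis offers Friedman or the following: "Repeated Measures ANOVA analysis will be used to compare the differences of continuous variables between baseline and 3 flow settings with each HFNC device". It names no trend test, flow-versus-flow contrast, post-hoc procedure or multiplicity rule. The significance level is 0.05.

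**The concern.** The hypothesis is ordered and compares flows. The planned test is an omnibus, and its wording allows two readings.

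- **Four conditions.** Baseline, 20, 40 and 60 L/min are four levels of one factor. The test can then be significant because HFNC differs from no HFNC, or because EELI drifts after the first period, with no difference between flows. The p-value also has no direction.
- **Three changes from baseline.** Each flow's change is compared across flows. Baseline cancels and the test is flow versus flow. The Sample size paragraph, which works in changes from baseline, supports this reading. The test is still unordered and has no follow-up rule.

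At stake is whether a significant result answers the primary question. On the first reading it need not. On the second it shows that flows differ but does not test a rise. On both, the flow comparison quoted in support could be picked after the results are known.

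**Working it through.** **Inputs.** From the documents: 26 subjects, alpha 0.05, 80% power, flows of 20, 40 and 60 L/min, baseline first. Assumed, because the documents give no within-subject SD: SD 1, independent normal errors of equal variance, one device.

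**The plan's own figure.** The difference behind the sample size is 1.44 − 1.12 = 0.32. N = 26 cannot be uniquely reproduced, because the type of bracketed spread, the within-subject correlation and the sidedness are not stated. Brackets read as IQRs (divided by 1.35), with a two-sided paired t-test, give 26 at correlation 0.8 but 59 at 0.5. So N can be neither confirmed nor called wrong, and this point does not rest on it. A paired t-test with n = 26 and 80% power corresponds to a standardised difference d = 0.57.

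**Four-condition reading, identical flows, HFNC on/off step s.** The RM-ANOVA noncentrality is λ = n·Σ(μⱼ − μ̄)²/σ². With means 0, s, s, s, the sum is 0.75s², so λ = 26 × 0.75 × s² = 19.5s², on 3 and 75 degrees of freedom. The Friedman and contrast columns are simulated (20,000 runs).

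| Step (SD) | λ | RM-ANOVA rejects | Friedman rejects | 60-minus-20 contrast rejects |
|---|---|---|---|---|
| 0.2 | 0.78 | 10% | 9% | 5% |
| 0.4 | 3.12 | 27% | 21% | 5% |
| 0.6 | 7.02 | 57% | 45% | 5% |
| 0.8 | 12.48 | 83% | 71% | 5% |

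RM-ANOVA on three change scores also stays at about 5%. Treating baseline as zero flow and testing a linear trend over 0/20/40/60 does not help: it rejects 10%, 26%, 51% and 75%.

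**Four-condition reading, drift only.** With no HFNC effect and drift of 0.05, 0.1 or 0.2 SD per period, the four-condition RM-ANOVA rejects 6%, 10% and 27% (simulated). The change-score test and the contrast stay at about 5%.

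**Direction.** At 0.3 SD per step, rising and falling responses are rejected about equally often: 80% and 81% by the four-condition test, and 45% each by the change-score test.

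**Change-score reading against the contrast.** For three flows λ = 26·Σ(μⱼ − μ̄)², on 2 and 50 degrees of freedom. The contrast is a paired t-test with d = (μ₆₀ − μ₂₀)/√2.

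| Flow means (SD) | λ | Change-score RM-ANOVA | d | Contrast |
|---|---|---|---|---|
| 0, 0.3, 0.6 (linear) | 26 × 0.18 = 4.68 | 45% | 0.6/√2 = 0.42 | 55% |
| 0, 0.6, 0.6 (plateau) | 26 × 0.24 = 6.24 | 57% | 0.42 | 55% |
| 0, 0.6, 0 (non-monotonic) | 26 × 0.24 = 6.24 | 57% | 0 | 5% |

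The contrast gains for a roughly linear rise, is level for a plateau, and loses for a non-monotonic response. If d = 0.57 spans the whole 20–60 L/min range with a linear rise, power is 72% for the change-score test and 80% for the contrast. If it applies to each 20 L/min step, both exceed 99.9%.

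**No follow-up rule.** When nothing differs, testing all three flow pairs unadjusted gives at least one false positive 12.6% of the time. All six pairs including baseline give 20.9% (both simulated).

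**The case against.** The strongest reply is that the large rejection rates depend on one reading. The Sample size paragraph speaks of changes from baseline, and if Data Analysis means the same, the step and drift problems vanish. That is correct, and those rates should be quoted only for the four-condition reading. The text does not say which is meant, and neither reading tests a rise.

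Second, comparing baseline with the flows is a stated outcome, and the four-condition test answers it properly. That also stands. The rates above are not false positives for that outcome; they mislead only if offered as evidence that flows differ. Outcomes ranks nothing as primary, so giving flow versus flow that status is an inference, though a sound one from the Abstract, Introduction and Sample size paragraph.

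Third, per-flow summaries will show direction, and reporting all three pairs involves no selection. This is fair: the gap is in the prespecified test, not in the data.

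A reader might infer more than the documents support:

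- **That EELI has no planned test**, because the bracketed list of continuous variables in Data Analysis omits it. That list concerns descriptive reporting, and the omission looks like drafting.
- **That the investigators will choose a comparison after seeing results.** The documents show only that they could.
- **That an omnibus test always has less power than a trend contrast.** The plateau and non-monotonic rows show otherwise.

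**Conclusion.** The point holds in a limited form. The primary hypothesis is an ordered comparison of flows, and the plan gives it only an unordered omnibus test with two possible readings and no flow contrast or follow-up rule. On the four-condition reading, a significant result can arise with identical flows: 10% to 83% of the time for on/off steps of 0.2 to 0.8 SD, against 5% for a flow-only contrast. On the change-score reading, the cost is a test without direction and about 10 points of power for a modest linear rise (45% against 55%). There is no loss for a plateau and an advantage for a non-monotonic response.

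All magnitudes rest on the assumed SD and on independent, equal-variance normal errors. They show the mechanism and do not estimate this trial's error rate. They do not show that N = 26 is wrong or that the baseline comparison is improper. This should be fixed before analysis; it is no more serious than that, since the data collected remain fully usable.

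**What to change.** In Data Analysis:

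1. Name EELI as the primary variable and state its scale. The contrast below is identical on raw EELI and on arithmetic change from baseline, but not on a ratio to baseline.
2. Prespecify one primary two-sided 0.05 within-subject contrast: each subject's 60-minus-20 L/min EELI difference. For three equally spaced flows this is the linear trend.
3. Report it with a 95% CI by paired t. If a rank test is wanted, use Wilcoxon signed-rank with the Hodges-Lehmann CI on the same differences. At 0.3 SD per step on normal data this has about 53% power, against 55% for t and 42% for Page's trend test.
4. State whether the contrast is run on the device average (one test) or per device with Holm's adjustment.
5. Report all three Holm-adjusted pairwise flow differences as secondary.
6. Keep baseline versus flows as a separate secondary analysis, labelled non-randomised.

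The cost is wording only: data collection, randomisation and N are unchanged. If the sample size is a paired comparison, the contrast has 80% power at d = 0.57 as a single test, or 70% at Holm's first per-device threshold of 0.025. With equal effects and independent devices (an assumption), Holm gives about 0.70 + 0.10 × 0.70 = 77% per device and 1 − 0.30² = 91% for at least one. The main downside is that the contrast alone can miss a non-monotonic response. The pairwise differences cover that: in the 0, 0.6, 0 case at least one Holm-adjusted pair is significant 52% of the time (simulated).

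### One primary question about flow and EELI is tested once per device, with no joint model, no flow-by-device test and no rule for which result is primary

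*Combined protocol and SAP*

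**What the plan says.** The Abstract defines the primary outcome by flow: "The primary outcome of this study is the lung aeration with different flow settings". It puts device among the secondary outcomes: "Secondary outcomes include the lung aeration with different devices". The Introduction gives one hypothesis that is not device-specific: "Our hypothesis is that as flow setting increases, lung aeration (EELI) will also increase". The Sample size paragraph does not mention device: "This study is a single group comparison study designed to compare the change of EELI with different flow settings during HFNC treatment".

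The Data Analysis section applies Friedman or repeated measures ANOVA to "compare the differences of continuous variables between baseline and 3 flow settings with each HFNC device", and compares the devices in a separate unpaired test. It sets one threshold, "value of < 0.05 will be considered statistically significant", and does not say how that threshold applies when the same question is tested twice.

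Two points must be inferred:

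- **EELI.** It is not among the variables named in brackets in Data Analysis. Outcomes lists EELI at baseline against the three flows, and the per-device test is the only flow comparison offered, so I take it to cover EELI.
- **Devices per volunteer.** Study Procedure and Data Collection read as though everyone uses both devices, but neither says so outright.

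**The concern.** A trial with one primary question should give one primary estimate. This plan gives two, from the same people at the same flows, and does not say whether one or both must be significant. Three things follow.

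- Each flow estimate is less precise than the collected data allow, because it leaves out the other device's readings.
- If one device reaches p<0.05 and the other does not, readers may conclude that the devices differ, although no planned analysis tests that.
- With two chances and no decision rule, the risk of a false-positive claim about flow exceeds 5%.

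**Working it through.** **Plan's own figure.** The Sample size paragraph cites "mean changes of EELI from baseline were 1.12 (0.8, 2.01) at 30 L/min and 1.44 (1.05, 2.16) at 50 L/min" and concludes "of 80%, the sample size is calculated to be 26". The difference is 1.44 - 1.12 = 0.32. The intervals are unlabelled. If they are interquartile ranges (assumption), the SDs are (2.01 - 0.80)/1.35 = 0.90 and (2.16 - 1.05)/1.35 = 0.82. The SD of a paired difference is √(0.90² + 0.82² - 2r × 0.90 × 0.82), where r, the within-person correlation, is not given. A two-sided paired t-test at 5% then needs 59 people at r=0.5, 37 at r=0.7 and 26 at r=0.8. So 26 can be neither confirmed nor refuted. It fits one paired contrast on one device with r about 0.79, that is, an SD of the difference of about 0.56. I use that SD below.

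**Data used by each test.** With both devices there are 6 on-HFNC periods and one baseline without a device, so 7 conditions. Each per-device test uses 3 + 1 = 4 of 7 (57%).

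**Which design?** For both devices, Study Procedure adds up to 5 + 20 + 6×20 + 5×5 = 170 min. For one device it is 5 + 20 + 3×20 + 2×5 = 95 min. The stated session is 3-4 hours, so both devices per person fits better.

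**Gain from combining.** Let ρ be the correlation between the two devices' flow differences (assumed; not in the documents). The device-averaged difference has variance 0.56² × (1+ρ)/2. Power comes from the noncentral t with n=26. The 95% CI half-width is 2.06 × SD/√26.

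| Analysis | SD | Power | Half-width |
|---|---|---|---|
| One device | 0.560 | 80% | 0.226 |
| Both, ρ=0.8 | 0.531 | 84% | 0.215 (5% narrower) |
| Both, ρ=0.5 | 0.485 | 90% | 0.196 (13% narrower) |
| Both, ρ=0 | 0.396 | 98% | 0.160 (29% narrower) |

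ρ=0 is a limit and is implausible for the same people at the same flows.

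**Disagreement.** With the same true difference of 0.32 on both devices, simulation gives one significant and one non-significant result in about 15% (ρ=0.8), 23% (ρ=0.5) and 32% (ρ=0) of trials. At ρ=0 this is 2 × 0.80 × 0.20 = 0.32.

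**False positives.** With no flow effect, the chance that at least one test is significant is 1 - 0.95² = 9.75% at ρ=0, about 9% at ρ=0.5 and about 8% at ρ=0.8.

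**Larger effects.**

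- *Baseline against 30 L/min:* 1.12/0.90 = 1.25 SD, with power above 99.9% at n=26.
- *The planned ANOVA with baseline:* simulated with changes of 1.12, 1.28 and 1.44, SD 0.86 and correlation 0.79 between flows, per-device power was about 100% and disagreement 0.0%.
- *20 to 60 L/min:* if the effect is linear (assumption), the difference is 2 × 0.32 = 0.64. Power is 99.99% at SD 0.56, and disagreement is near 0%. If the variance doubles, power is about 98% and disagreement at most 2 × 0.977 × 0.023 = 4.5%.

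**The case against.** The strongest reply is that the 80% power and the disagreement rates describe a single 0.32 contrast, not the test that is planned. That contrast is between 30 and 50 L/min, and the trial uses neither flow. The planned test includes baseline, where the effect is large enough that both devices should be clearly significant. This stands, and it limits the disagreement figures to a 20 L/min step. It does not remove the concern. A test that includes baseline can be significant merely because HFNC differs from no HFNC, whereas the hypothesis and the sample size concern differences between flows.

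Per-device reporting is also legitimate, because the Introduction treats the performance of both devices as unknown. That stands too, and the fix keeps it as secondary.

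A reader might infer three stronger claims that the documents do not support:

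- *Half the EELI data are discarded.* Each test uses 4 of 7 conditions, and the other device's readings are analysed in their own test.
- *The two results will often conflict.* That depends on the effect size and on ρ, and the documents do not settle either. For large effects, conflict is rare.
- *Each test has only half the sample.* With 13 people per device, power for 0.32 would be about 47%. The session length and Data Collection point to both devices per person, which would make that figure irrelevant.

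**Conclusion.** The concern holds in a limited form. One primary flow question is analysed as two separate tests, with no joint model, no interaction test and no rule for choosing between the results. For a 20 L/min step, the likely loss is the gap between 80% and about 84-90% power, with an interval 5-13% narrower if the devices were combined. Without a decision rule, the chance of at least one false-positive flow result is about 8-10% rather than 5%. Disagreement of about 15-23% applies only at that effect size.

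These figures rest on an SD of 0.56 back-solved from n=26 and 80% power, an assumed ρ of 0.5-0.8, and every volunteer using both devices. The missing primary estimate and the missing interaction test depend on none of these. The trial would remain interpretable, but the plan should be changed before the data are analysed.

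**What to change.** Name EELI in Data Analysis and make its primary analysis one linear mixed model on change from the no-HFNC baseline at 20, 40 and 60 L/min.

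- **Fixed effects:** flow, device, flow-by-device and period.
- **Random effects:** participant and participant-by-flow.
- **Primary result:** the flow contrasts averaged over devices, with 95% CIs.
- **Secondary results:** per-device flow effects and the flow-by-device term.

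Using change from baseline deals with the fact that baseline has no device level; baseline cancels from contrasts between flows. If a non-normal fallback is wanted, average each person's two device readings at each flow and apply the Friedman test already planned.

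State that each participant uses both devices. If they do not, keep the model with device as a between-participant factor; participant-by-flow then cannot be separated from residual error and drops out.

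The cost is analysis wording only, with no new data or participants. The small downside is that an averaged effect is less direct if the devices truly differ, which the interaction and per-device estimates would show.
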